9.1.3. Maximum Severity of Symptoms at DBPCFC

Maximum severity of symptoms at the DBPCFC will be summarized at the 2000 mg, 1000 mg, and 600 mg levels. Symptom severity is determined according to the CoFAR scale at 5 levels: 1-Mild, 2-Moderate, 3-Severe, 4-Life Threatening, and 5-Fatal. Analysis is done on 4 levels: 0-None, 1-Mild, 2-Moderate, 3-Severe or higher (severe, life threatening, fatal). Subjects who experience no symptoms will be assigned a severity of 0-None. Symptom severity data is collected at each challenge dose of peanut protein during the DBPCFC (3 mg, 10 mg, 30 mg, 100 mg, 300 mg, 600 mg, 1000 mg, and 2000 mg). The maximum severity of symptoms observed in the DBPCFC at the specified dose (2000 mg, 1000 mg, or 600 mg) or lower will be used for each subject.

The number and percent of subjects will be presented by maximum severity for the specified challenge dose levels at the Exit DBPCFC for each group/cohort and at the maintenance DBPCFC for Group 1 for subjects who complete the maintenance DBPCFC.

9.1.4. Use of Epinephrine as a Rescue Medication at DBPCFC

The number and percentage of subjects using Epinephrine as a rescue medication at the Exit DBPCFC will be summarized by type of challenge (peanut protein or placebo) for each group/cohort. Similarly, the number and percentage of subjects using Epinephrine as a rescue medication at the maintenance DBPCFC will be summarized by type of challenge (peanut or placebo) for Group 1.

The number and percentage of subjects using epinephrine use as a rescue medication will also be summarized by each dose level (up through 2000 mg, up through 1000 mg, up through 600 mg, up through 300 mg, etc.) at the Exit peanut DBPCFC for each group/cohort and at the maintenance peanut DBPCFC for Group 1.

The number of epinephrine doses as a rescue medication will be summarized by dose level (up through 2000 mg, up through 1000 mg, up through 600 mg, etc.) during the Exit peanut DBPCFC for each group/cohort and during the maintenance peanut DBPCFC for Group 1. Doses will be categorized as 0 doses, 1 dose, 2 doses, and 3 or more doses.

Listings of all Epinephrine use will be provided.

9.1.5. Changes in Peanut-specific IgE, total IgE and peanut-specific IgG₄

Blood samples will be collected to measure ps-IgE, ps-IgG4 levels, and total IgE. Ps-IgE/IgG4 ratio will be calculated, listed by subject, and summarized by visit and group/cohort. Results outside the limits of quantification will be displayed as less than the lower limit of quantification (LLOQ), or greater than the upper limit of quantification (ULOQ), as appropriate. These values will be summarized as either the LLOQ or the ULOQ. If the ps-IgE or ps-IgG4 is outside of the limits of quantification, the ps-IgE/IgG4 ratio will be calculated using the LLOQ or ULOQ as appropriate.

Summary statistics, including geometric means and geometric standard deviations, will be presented by visit and group/cohort, and change from baseline to each visit will also be presented.

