9.2.2 Secondary Endpoints

- Frequency of anaphylaxis
- Frequency of use of epinephrine as a rescue medication
- Frequency of AEs leading to withdrawal of AR101
- Frequency of AEs in each treatment regimen leading to discontinuation of extended interval dosing
- Frequency of GI AEIs
- Frequency of accidental food allergen exposure
- In subjects with asthma, change in asthma control using the Asthma Control Test questionnaire (see [Appendix 2](#))
- Frequency of all above safety endpoints by treatment period
- The proportion of subjects in each regimen tolerating ≥ 1043 mg cumulative of peanut protein during their EM Exit DBPCFC
- The proportion of subjects in each regimen who tolerate ≥ 443 mg cumulative of peanut protein during their EM Exit DBPCFC
- The proportion of subjects in each regimen who tolerate 4043 mg cumulative of peanut protein during their EM Exit DBPCFC

- Maximum tolerated dose and change from baseline* at Post-Maintenance** and each EM Exit DBPCFC
- Maximum severity of symptoms at each challenge dose at Post-Maintenance** and each EM Exit DBPCFC
- Frequency of use of epinephrine as a rescue medication at the Post-Maintenance** and each EM Exit DBPCFC
- Change in QoL as assessed by the FAQLQ and the FAIM questionnaire
- Satisfaction with AR101 treatment as assessed by the TSMQ-9 questionnaire and additional questions
- Changes in peanut-specific serum IgE and IgG4 levels
- Changes in peanut skin prick test (SPT) wheal diameter

*Baseline is defined as the Screening DBPCFC from ARC003 for both treatment groups.

**Post-Maintenance is defined as the ARC003 Exit DBPCFCs for Group 2.

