6. GENERAL ASPECTS FOR STATISTICAL ANALYSIS

6.1. STATISTICAL NOTATION AND METHODOLOGY

Unless stated otherwise, the term “descriptive statistics” refers to the number of subjects (n), mean, median, standard deviation, minimum, and maximum for continuous variables and frequencies and percentages for categorical variables.

Unless specified otherwise, the denominator for percentages for categorical data will be based on the number of subjects or observations with non-missing data appropriate for summary purposes. The denominator for percentages for incidence data (such as adverse events) will be based on the number of subjects in the analysis population “at risk”. Select ordinal data may be summarized using both descriptive statistics and counts and percentages of subjects in each category, as appropriate.

Minimum and maximum values will be presented at the precision of the original value, means, medians will be rounded to 1 decimal place greater than the precision of the original value, standard deviations and standard errors will be rounded to 2 decimal places greater than the precision of the original value. Percentages will be rounded to 1 decimal place. Percentages that round down to 0 or up to 100% will be displayed as “<0.1%” and “>99.9%”, respectively. Other statistics (e.g., confidence intervals (CIs)) will be presented using the same general rules outlined above, or assessed for the most appropriate presentation based on the underlying data.

Unless otherwise noted, values reported as greater than or less than some quantifiable limit (e.g., “< 1.0”) will be summarized with the sign suppressed in summary tables and figures, using the numeric value reported. Data will display on subject listings to include the sign.

Summary tables will be presented by group/cohort displayed as Group 1 and Group 2 with Cohort 1, Cohort 2, Cohort 3A, Cohort 3B, and Cohort 3C. For disposition, demographic, and other summaries of baseline and history data, a Total column for both groups combined will be included. For any summaries of events such as adverse events or concomitant medications, event incidences will be summarized in the Safety population separately for the following group/cohort study periods:

- Group 1: IDE and Up-Dosing, all QD Maintenance (including extended maintenance), Overall
- Group 2 Cohort 2: QOD, BIW, and Overall
- Group 2 Cohort 1 (includes QD only)
- Group 2 Cohort 3A (includes QD only)

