7.5. DATA DERIVATIONS AND DEFINITIONS

The following definitions and derivations will be used throughout this study:

- Study day is calculated relative to the first dose date in ARC004 as (assessment date – first dose date + 1) for assessments and visits performed on or after the first dose date, and (assessment date – first dose date) for assessments and visits prior to the first dose date.
- In this follow on study, baseline is defined as the last non-missing value prior to the first dose of study treatment in the study where study product is first received. For Group 1 patients (those previously on placebo in ARC003), baseline is relative to first dose of AR101 in study ARC004. For Group 2 patients (those continuing on AR101 therapy from ARC003), baseline is relative to first dose of AR101 in study ARC003. If no ARC004 data were entered for a Group 1 subject, use the last available ARC003 data prior to first dose of AR101 in ARC004. For food challenge end points, the ARC003 exit food challenge will serve as the baseline for both groups.

Sponsor: Aimmune Therapeutics, Inc.

Protocol: ARC0004

Version: Version 1.0, 10Jul2019

- Change from baseline is calculated as observed value after the first dose – baseline value.
- Group 1 Initial Dose Escalation period is defined as the time period beginning with the date and time of the first dose of study product in clinic and ending with the date of the last dose of study product taken prior to Up-dosing.
- Group 1 Up-dosing period is defined as the time period beginning with the date and time of the first home dose of study product at 3 mg, and ending with the date and time of first in-clinic dose at 300 mg. This period will be, ideally, 22 weeks in duration, but may be extended to a maximum of 40 weeks to accommodate dose reductions and re-escalations, if necessary.
- Group 1 Maintenance period is defined as the time period beginning with the date and time of the first home dose of study product at 300 mg and ending with the date of the last dose of study product taken prior to the maintenance DBPCFC. The maintenance period lasts approximately 24 weeks.

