9.1.2. Maximum Tolerated Dose at Exit DBPCFC

The DBPCFCs are based on a modified Practical Allergy (PRACTALL) dosing regimen as described in the ARC003 protocol (Section 3). ARC004 DBPCFCs will include a single highest dose of 2000 mg, whereas ARC003 included a single highest dose of 1000 mg at Exit. With the exception of the 600 mg and 2000 mg doses, the modified PRACTALL doses are approximately on a logarithmic scale.

Sponsor: Aimmune Therapeutics, Inc.

Protocol: ARC0004

Version: Version 1.0, 10Jul2019

The MTD will be summarized at screening and exit along with fold increase from screening for each group/cohort. Subjects who did not tolerate any dose will be assigned an MTD of 0.3 mg to calculate fold change. Changes from screening to the maintenance DBPCFC will be summarized similarly for Group 1 for subjects who complete the maintenance DBPCFC.

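### SAP 9.1.5 names no scale for change in the immunoglobulins, so SAP 7.5 makes it a raw difference, at odds with the geometric summaries of the levels

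*SAP*

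**What the plan says.** Protocol 9.2.2 lists "Changes in peanut-specific serum IgE and IgG4 levels" as a secondary endpoint, and SAP 3.2 repeats it. Together with the skin prick test, it serves the objective on long-term immunologic effects.

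SAP 9.1.5 treats the levels multiplicatively: "Summary statistics, including geometric means and geometric standard deviations, will be presented by visit and group/cohort". For change it adds only that "change from baseline to each visit will also be presented".

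The one definition of change is the general rule in SAP 7.5: "Change from baseline is calculated as observed value after the first dose – baseline value". Neither 9.1.5 nor SAP 11 (changes from the protocol) makes an exception for the immunoglobulins.

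Three other provisions bear on the point:

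- SAP 6.1 sets the default descriptive statistics: "the number of subjects (n), mean, median, standard deviation, minimum, and maximum for continuous variables".
- SAP 9.1.2 uses a fold scale for a different variable: "The MTD will be summarized at screening and exit along with fold increase from screening for each group/cohort".
- SAP 9.1.5 says of results outside the quantification limits: "These values will be summarized as either the LLOQ or the ULOQ". The ratio is computed from the same substituted values.

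**The concern.** A geometric mean and SD are chosen when a marker is thought to vary by multiples. The matching measure of change is then a ratio. A difference can be zero or negative, so the geometric statistics in 9.1.5 cannot be applied to change as 7.5 defines it. The programmer is left with the arithmetic mean, SD and median of raw differences, or with a scale chosen after the data are seen.

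Two things are at stake.

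- **Precision.** If the markers are strongly skewed, the mean raw change is weighted towards the subjects who start highest on that marker, and its standard error grows.
- **Comparability.** Two cohorts with the same proportional response but different starting levels show different raw changes. Cohorts 1, 2 and 3 are filled in order of entry (protocol 3), so their baselines may differ. SAP 6.2 plans no modelling that could adjust for this.

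**Working it through.** **Figures in the plan.** Neither document states an expected change, variance or distribution for these markers, so there is no figure to reproduce. Everything below is illustration under stated assumptions.

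**Inputs from the documents.** Protocol 7.8.3 plans 50 subjects in Cohort 2 and 175 across 3A, 3B and 3C: 175/3 ≈ 58 each.

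**Assumed inputs.** Lognormal baseline, median 50 units, geometric SD 2, 3, 5 or 8. Follow-up = baseline × lognormal fold change, with median 0.7 and log-SD 0.5.

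**1. Dependence on starting level.** Apply a fold change of 0.7 to two subjects. From 50: 0.7 × 50 − 50 = −15. From 100: 0.7 × 100 − 100 = −30. The proportional response is the same, but one raw change is twice the other.

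**2. Weight of high-baseline subjects.** If every subject had the same fold change, the top 10% by baseline would supply a share 1 − Φ(1.2816 − σ) of the summed raw change, where σ is the log-SD of baseline:

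| σ | geometric SD = exp(σ) | share from top 10% |
|---|---|---|
| 0.5 | 1.65 | 22% |
| 1.0 | 2.72 | 39% |
| 1.5 | 4.48 | 59% |
| 2.0 | 7.39 | 76% |

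**3. Precision at n = 58, with variable fold change (simulation).** The benchmark on the log scale is |ln 0.7| / (0.5/√58) = 0.3567/0.0657 = 5.4, whatever the baseline spread.

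| Baseline geometric SD | share of total change from top 6 of 58 | typical mean raw change / its SE (absolute) | mean raw change has wrong sign |
|---|---|---|---|
| 2 | 29% | 3.1 | 0.7% |
| 3 | 44% | 2.5 | 2.8% |
| 5 | 63% | 1.9 | 7.2% |
| 8 | 78% | 1.6 | 10.2% |

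The third column is the median across simulated cohorts of each cohort's own mean divided by its own SE. The median raw change had the wrong sign in about 0% of runs at every spread.

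**4. Comparability of two cohorts (58 and 50).** Every subject's value is halved exactly and both cohorts are drawn from the same baseline distribution. The geometric mean fold change is 0.50 in both. The raw summaries differ by chance in baseline alone (95% range of the between-cohort ratio):

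| Baseline log-SD | ratio of mean raw changes | ratio of median raw changes |
|---|---|---|
| 1.0 | 0.62 to 1.64 | 0.63 to 1.59 |
| 1.5 | 0.39 to 2.54 | 0.49 to 2.00 |
| 2.0 | 0.22 to 4.53 | 0.39 to 2.54 |

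The median therefore resists outliers but not differences in starting level.

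**5. Truncation.** Suppose a ULOQ of 100 (assumed). A true fall from 300 to 90 is a fall of 1 − 90/300 = 70%. It is recorded as 100 to 90, a fall of 10%. The recorded ratio is 0.90 in place of 0.30, so a fold scale shows the same distortion.

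**The case against.** The strongest reply is that this is a gap in wording with limited consequences. Section 9.1.5 does not itself call the change a difference; that follows only from the general rule. Section 9.1.2 uses a fold increase without declaring an exception to 7.5, so 7.5 may not be meant to bind everywhere. That is fair, and the charge is that the scale is unstated and the default is a difference.

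A reader might infer that a few high-IgE subjects will determine the result. The documents do not support that. They give no distribution, and at low skewness the effect is modest. It concerns the mean and SD, while the median is reported by default. For ps-IgG4 or the ratio, the influential subjects would be those high on that marker, not on IgE. A mean with the wrong sign would usually show as a disagreement with the median.

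A reader might also infer that cohorts cannot be compared at all. That is too strong. Geometric means by visit and cohort allow a ratio to be formed by hand. With 10% of values missing at random, its 95% range is 0.59 to 0.83 at geometric SD 3 and 0.58 to 0.85 at geometric SD 5, against about 0.62 to 0.80 for the paired ratio. It is usable, but it is unpaired, comes without an interval, and could be biased if samples are not missing at random. SAP 6.4 plans no formal comparison, so no test or decision rule is affected.

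Out-of-range results are displayed as such, so affected pairs can be found in the listings. Only a tabulated count is missing.

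**Conclusion.** The point holds as a mismatch of scale. Followed as written, the plan summarises levels geometrically and change as a raw difference, and nothing in the SAP resolves this. The raw change is not reliably comparable between cohorts with different baselines, on the mean or on the median.

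The loss of precision and the weight of high-baseline subjects are conditional on skewness. They are substantial if the baseline geometric SD is 3 or more and smaller at 2. All these sizes assume lognormal markers, a median fold change of 0.7 and a within-subject log-SD of 0.5; the direction does not depend on the exact values.

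Truncation at the quantification limits is a separate matter that a fold change does not cure. Because the endpoint is descriptive and secondary, the severity is minor.

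**What to change.** In SAP 9.1.5, as a stated exception to 7.5, define change for ps-IgE, total IgE, ps-IgG4 and the ps-IgE/IgG4 ratio as each subject's visit value divided by that subject's baseline value. Report, by visit and group/cohort, the geometric mean of that ratio with a descriptive 95% CI (computed on the log scale and back-transformed) and the median ratio. Use only subjects with both values and show their number.

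Separately, tabulate for each visit how many pairs contain a value set to the LLOQ or ULOQ, and give the fold change with and without those pairs.

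The cost is a few lines of SAP text, a log transformation in programming and a second display for the affected pairs. No new data are needed.

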9.1.6. Peanut Skin Prick Test

Results from the SPT will be listed, including test date and time, and measurements of the mean wheal diameter (in mm) of the following: peanut wheal (long axis), peanut erythema/flare (short axis), saline wheal (long axis), saline-glycerin erythema/flare (short axis), histamine wheal (long axis), and histamine erythema/flare (short axis).

A derived mean wheal diameter score will be calculated as the average of the long and short axis from the peanut wheal minus the average of the long and short axis from the saline wheal. Summary statistics for the derived SPT mean wheal diameter will be presented at each visit by group/cohort and change from baseline to each visit will be presented.

9.1.7. Quality of Life Assessments

Quality of life assessment using the FAQLQ and the FAIM questionnaires will be performed prior to the start of treatment and after the Exit DBPCFC or early discontinuation.

Separate FAQLQ and FAIM instruments are administered based on the subject's age group. Parent versions are also administered for all subjects. Due to differences between the various instruments, separate summaries will be provided by age group and person who completed the questionnaire (i.e., subject or parent).

FAQLQ:

The FAQLQ is a self-report instrument that is intended to assess the effect of food allergy on the subject's quality of life. Evaluations are done by the subject using a different form by age group (8-12 years and 13-17 years) ([Flokstra-de Blok, 2008](#); [Flokstra-de Blok,](#)

Sponsor: Aimmune Therapeutics, Inc.

Protocol: ARC0004

Version: Version 1.0, 10Jul2019

[2009](#)). Evaluations are also done by the parent/caregiver using a different form by age group (4-6 years, 7-12 years, and 13-17 years) ([DunnGalvin, 2008](#)).

Each question is presented on a scale from 0 (not at all) to 6 (extremely) and scored from 1 to 7. The number of items and domains varies by instrument administered. For reporting, the domains for each included form are as follows:

Adult form ≥ 18 –

- a) Allergen Avoidance and Dietary Restrictions
- b) Risk of Accidental Exposure
- c) Emotional Impact
- d) Food Allergy Related Health

Teen form 13-17 –

- a) Allergen Avoidance and Dietary Restrictions
- b) Risk of Accidental Exposure
- c) Emotional Impact

Child form 8-12 –

- a) Allergen Avoidance and Dietary Restrictions (Allergen Avoidance + Dietary Restrictions)
- b) Risk of Accidental Exposure
- c) Emotional Impact

Parent form teen 13-17 –

- a) Social and Dietary Limitations (Dietary Restrictions + Social Restrictions)
- b) Food Anxiety
- c) Emotional Impact

Parent form 7-12 –

- a) Social and Dietary Limitations
- b) Food Anxiety
- c) Emotional Impact

Parent form 4-6 –

- a) Social and Dietary Limitations
- b) Food Anxiety
- c) Emotional Impact

For each domain, the domain average score is the arithmetic average of the non-missing items comprising the domain. For any respondent and form, the domain score algorithms above should be derived only if more than half the items comprising that domain score have valid responses. For all forms, the total score will be calculated as the average of the domain averages: (average a + average b + average c) / 3. Total scores should not be

Sponsor: Aimmune Therapeutics, Inc.

Protocol: ARC0004

Version: Version 1.0, 10Jul2019

computed if one or more of the domain scores comprising the total are missing. For FAQLQ-PF 4-6, if items are completed that were not included for this age group, these items will not be included towards the scoring. For FAQLQ-AF, the fourth domain of Food Allergy Related Health is not included in the total score calculation.

For child, teen, and all parent forms, descriptive statistics on the total and domain scores along with their changes from baseline will be provided. Data will be summarized for the safety population separately by questionnaire age group and responder (subject or caregiver).

Listing of the raw scores as recorded in the CRF, domain scores, and total scores will be provided, sorted by age group, group/cohort, and subject ID.

FAIM:

The FAIM is a self-report instrument that is intended to reflect the perception of food allergy severity and related risk as evaluated by the subject using a different form by age group (8-12 years and 13+ years) ([van der Velde, 2010](#)). Evaluations are also done by the parent/caregiver using a different form by age group (4-12 years and 13-17 years). The instrument consists of 6 questions (4 expectation of outcome questions and 2 disease severity questions). The parent/caregiver versions include questions related to perception of disease severity and expectation of allergen exposure outcome. The parent/caregiver form includes 8 questions for subjects aged 4-12 years and 4 questions for subjects aged 13 to 17 years.

The FAIM is scored on a 7-point scale from 1 (limited severity perception) to 7 (greatest severity perception). For parent form item 4 (including 1.4, 2.4, and 4) where responses are given from greatest severity perception to most limited severity perception, the scale should be reversed to range from most limited to most severe for scoring purposes. That is, where the question is positively worded as “Effectively treating him/herself...” a response of “Extremely unlikely” should be scored as a 7 rather than a 1.

Domains for the FAIM are to be defined as follows:

Teen and adult form –

- a) Expectation of outcomes (includes items 1-4)
- b) Risk of Accidental Exposure (includes item 5)
- c) Emotional Impact (includes item 6)

Child form –

- a) Expectation of outcomes (includes items 1-4)
- b) Risk of Accidental Exposure (includes item 5)
- c) Emotional Impact (includes item 6)

Sponsor: Aimmune Therapeutics, Inc.
Protocol: ARC0004
Version: Version 1.0, 10Jul2019

Parent form teen –

- a) Parent expectation of outcomes (includes all items on form 1-4)

Parent form 4-12 –

- a) Parent expectation of outcomes (includes items 1.1-1.4)
- b) Child expectations of outcomes (includes items 2.1-2.4)

Domain scores are the arithmetic average of the non-missing items comprising a domain. For child and teen/adult forms, a total score is defined as the arithmetic average of all the non-missing items. For any respondent and form, the domain and total scores should be calculated only if more than half the items comprising that domain/total score have valid responses.

For subjects 4-17, descriptive statistics for domain scores and for non-parent forms the total scores along with their changes from baseline will be tabulated. Data will be summarized for the safety population separately by questionnaire age group and responder (subject or parent).

Listing of the transformed scores, domain scores, and total scores will be provided, sorted by age group, group/cohort, and subject ID.

